1.0 SUMMARY OF STUDY (Abstract with a maximum of 300 words)

The ideal local anesthetic (LA) solution for activation of a labor epidural would be one that provides rapid pain relief with minimal side effects such as hypotension and motor blockade. Commonly used LA in obstetrics includes bupivacaine and lidocaine. Due to either slow onset (bupivacaine)¹ or a higher incidence of hypotension (lidocaine)² neither meet the criteria for the ideal LA. This is where the thought of combining the two LA solutions arises. Maybe a 1:1 mix will produce a faster onset than bupivacaine with a lower incidence of hypotension than lidocaine.

We hypothesize that lidocaine will achieve a T₁₀ level the fastest when compared to bupivacaine and bupivacaine plus lidocaine. The bupivacaine plus lidocaine onset of action will not be significantly faster when compared to bupivacaine. Given the concentration of the bupivacaine, less hypotension and motor block will be present when compared to the lidocaine and bupivacaine plus lidocaine. The bupivacaine plus lidocaine will offer no increased benefit of having a faster onset with less hypotension or motor blockade than either LA solution alone.

We will conduct a prospective, randomized, double-blind study on 45 patients receiving a lumbar epidural for labor analgesia. After a negative test dose, the anesthesia provider will administer the randomized LA via epidural catheter: 10 mL 0.125% bupivacaine, or 10 mL 1% lidocaine, or 5 mL 0.125% bupivacaine plus 5 mL 1% lidocaine. The investigator will assess the patients sensory level to pin prick and ice, degree of motor block, blood pressure, heart rate, and fetal heart rate at intervals of 0, 5, 10, 15, and 20 minutes. Primary outcome will be the time to achieve a T₁₀ level. Secondary outcomes include the total spread of the block, onset and degree of motor block, incidence of hypotension and need for vasopressor therapy, and fetal well-being.

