2.0 BACKGROUND & RATIONALE

The most common and effective method for controlling labor pains is a local anesthetic infusion through a lumbar epidural.¹ To achieve adequate pain control during the first stage of labor – onset of contractions to complete cervical dilation – nerve fibers up to the T₁₀ dermatome must be anesthetized.¹ When a patient is in active labor and an epidural catheter is placed, the anesthesiologist must activate the epidural by administering LA through the epidural to promote spread of the LA in the epidural space to anesthetize the nerve fibers involved in the conduction of labor pains. The ideal LA to achieve this goal is one that would allow for the fastest onset to achieve quick pain relief with the fewest side effects. Common side effects of LA used in labor epidurals include maternal hypotension and motor blockade.³

Two commonly used LA to provide labor analgesia are bupivacaine and lidocaine. When low concentrations – 0.125% bupivacaine and 1% lidocaine – are used for labor analgesia, both of these LA can be administered safely with very little concern of major adverse effects associated with LA toxicity. However, more common side effects such as maternal hypotension requiring vasopressor therapy and motor blockade can often occur.³

Though both are amide LA, bupivacaine and lidocaine display different properties that give each an advantage in certain situations. Lidocaine's onset of action is faster than that of bupivacaine's (5-15 vs. 10-20 minutes for epidural injection).¹ Whereas bupivacaine has a longer duration of action (180-300 vs. 60-180 minutes).¹ Through a sympathetically mediated veno- and vaso-dilation, both LA commonly cause hypotension. Although the time to develop hypotension was not noted, several studies have noted a higher incidence of hypotension with the administration of epidural lidocaine vs. bupivacaine.^{2,4}

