4.0 OBJECTIVE(S) & HYPOTHESIS

Our overall goal is to determine which commonly used LA or combination of LA demonstrates the most ideal properties in a patient receiving an epidural for labor pains. As anesthesiologists, we strive to provide a fast-acting and safe anesthetic in these patients to elicit rapid pain relief in laboring mothers.

Currently, there are several ways in which we activate a labor epidural with LA. Three of the more common LA solutions used are 1% lidocaine, 0.125% bupivacaine, or a combination of bupivacaine and lidocaine. In a prospective, randomized, double-blinded study, we plan to determine if one solution is more superior to the others.

Briefly, after consent is obtained, a standard anesthesia provider will place a labor epidural in regular fashion. After a negative test dose, the anesthesia provider will then administer the study solution the patient was randomized to receive (10 mL of 0.125% bupivacaine, 10 mL of 1% lidocaine, or 5 mL of 0.125% bupivacaine plus 5 mL of 1% lidocaine). The standard epidural infusion bag will then be started by the anesthesia provider. Both the patient and investigator will be blinded to the study. Once the study drug bolus has been given, the investigator will collect the data.

Data to be collected will be: sensory level (by pin prick and ice), degree of motor block by using a modification of Bromage's scale³ (see section 8.0), maternal heart rate (HR) and blood pressure (BP), the need to administer a vasopressor agent (phenylephrine or ephedrine) to treat hypotension, the amount of vasopressor given, and fetal heart rate (FHR). Starting with the initial bolus (Time 0 or T₀), data will then be collected 5, 10, 15, and 20 minutes after the bolus.

The primary outcome for this study is the time it takes to achieve a T₁₀ dermatome level by pinprick (which signifies an adequate epidural level for labor analgesia).

Secondary outcomes include: the total spread (both cephalad and caudal) of the LA (dermatome level to be determined by pin prick and ice), degree of motor block, incidence of maternal hypotension defined as a BP >20% decline from baseline, the need to administer a vasopressor to treat the hypotension, the amount given, and if there is any change in fetal status by monitoring FHR.

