5.0 INTERPRETATION OF EXPECTED RESULTS

06_18_2014

If we see a significant decrease in time to achieve a T₁₀ dermatome level with the bupivacaine and lidocaine mixture compared to the bupivacaine only solution, then that would imply that the addition of the lidocaine did speed up the onset of action of the LA solution we used to activate the epidural. We would also need to account for each LA solution's side effect profile. By measuring the incidence of hypotension and degree of motor blockade, we will be able to determine if one solution's side effect profile is more favorable. By determining the advantages vs. disadvantages of each solution, we would be able to recommend the most ideal LA solution of those studied as the solution best suited for activation of labor epidurals.

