8.0 STUDY INTERVENTIONS/PROCEDURES

Our study will be a prospective, randomized, double-blind study comparing three commonly used methods to activate a labor epidural. These three solutions will be 10 mL of 0.125% bupivacaine (B), 10 mL of 1% lidocaine (L), and 5 mL of 0.125% bupivacaine plus 5 mL of 1% lidocaine (BL). The primary outcome of the study will be measurement of the time it takes to achieve an adequate anesthetic level (T₁₀) to control labor pains. Secondary outcomes include: the total level achieved, degree of motor blockade, incidence of maternal hypotension (>20% decline from baseline), the need for vasopressor use, the amount of vasopressor needed, and fetal

well-being (monitoring of FHR). Since LA will be required to produce our primary outcome, no group will receive a placebo. The three groups (B), (L), and (BL) will be compared to each other.

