Pregnant patients who are admitted to the L&D floor at the WIC and have none of the above mentioned exclusion criteria will be approached about enrolling in the study. Informed consent will be obtained before any obstetric intervention occurs that might cause pain or altered mental status to the patient. Once the patient requests for her epidural to be placed, the investigator will be notified. Any qualified anesthesia provider will then place the labor epidural. Per our routine practice, the epidural will be placed in the L₂₋₃ or L₃₋₄ interspace, secured at plus 5 cm from the loss of resistance distance at the skin, and the routine test dose of 3 mL of 1.5% lidocaine with 1:200,000 epinephrine will be administered to rule out spinal or intravascular placement of the epidural catheter. After the epidural catheter is deemed safe to use (from a negative test dose), the anesthesia provider will administer the LA solution the patient has been randomized to receive: 10 mL (B), 10 mL (L), or 10 mL (BL), and the standard LA infusion will be connected to the epidural and started. The time that the LA bolus occurred will be marked as T₀. The patient's BP, HR, anesthetic level to pin prick and ice, degree of motor blockade, and FHR will be recorded at that time by the blinded investigator. Motor blockade will be tested by a modification of Bromage's scale where: 0 = the ability to maintain a leg lift for prolonged periods; 1 = the ability to lift legs briefly; 2 = the ability to bend knees; 3 = the ability to wiggle toes; 4 = no movement in lower extremities.³ Then at intervals of 5, 10, 15, and 20 minutes, the investigator will document the above mentioned data with the addition of any vasopressor (phenylephrine or ephedrine) required to treat maternal hypotension and the dose.

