11.0 STATISTICAL CONSIDERATIONS

The outcome Y is time to T_{10} sympathectomy. An ANOVA will be used to estimate the overall difference of the mean onset times between study groups. An estimate of onset times of 5, 6 and 7 minutes and an estimated variance of 1 min is based on the existing literature.¹² Using an alpha = 0.05, 80% power and a calculated effect size of $f = 0.82$, the total sample size sample size based on an ANOVA is N=18. Accounting for some prediction inaccuracy, we propose a target sample size of N=45, n=15 per study group.

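### Time to T10 is read only every 5 minutes but sized on means of 5, 6 and 7 minutes with SD 1; at those inputs the outcome is almost binary and power for mixture versus bupivacaine falls from about 75% to about 15%.

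*Combined protocol and SAP*

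**What the plan says.** Section 4.0 defines the endpoint: "The primary outcome for this study is the time it takes to achieve a T₁₀ dermatome level by pinprick". The same section sets the schedule: "data will then be collected 5, 10, 15, and 20 minutes after the bolus". The summary in section 1.0 ("at intervals of 0, 5, 10, 15, and 20 minutes") and section 8.0 ("Then at intervals of 5, 10, 15, and 20 minutes, the investigator will document the above mentioned data") agree with it. No section describes readings between these checks, a record of the exact minute at which T10 is reached, or an analysis for grouped times.

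Section 11.0 treats the outcome as a continuous time compared by ANOVA. Its inputs are "An estimate of onset times of 5, 6 and 7 minutes and an estimated variance of 1 min", alpha 0.05, 80% power and f = 0.82. These give N=18, which is raised to 45 (15 per group) to allow for inaccurate prediction.

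The protocol wants more than the overall test. Section 8.0 states: "The three groups (B), (L), and (BL) will be compared to each other". The section on interpretation of expected results rests the question of whether lidocaine speeds onset on a shorter time to the T10 "dermatome level with the bupivacaine and lidocaine mixture compared to the bupivacaine only solution".

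**The concern.** The plan looks for 1-minute differences with a 5-minute measuring interval. A patient who reaches T10 at 5.2 minutes and one who reaches it at 9.8 minutes are both recorded at 10. With assumed means just at or above the 5-minute check and an SD of 1, the recorded outcome is close to a yes/no answer to whether T10 was present at 5 minutes. The sample-size calculation does not reflect this.

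What is at stake is the comparison of the mixture (BL) with bupivacaine alone (B). Section 4.0 predicts that BL will not be significantly faster than B. If the schedule hides most of a real 1-minute difference, the trial can appear to confirm that prediction whatever the drugs do. Onset times that were not observed cannot be recovered after enrolment.

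**Working it through.** **Inputs.** From section 11.0: means 5, 6 and 7 minutes, variance 1 (SD 1), alpha 0.05, 15 per group. From sections 1.0, 4.0 and 8.0: checks at 5, 10, 15 and 20 minutes after the bolus. Assumptions added here: normal onset times; each time recorded at the first check at or after true onset; lidocaine (L) = 5, BL = 6, B = 7; two-sided unadjusted two-group t-tests for pairs, because the plan names no pairwise test. L = 5 follows the hypothesis that lidocaine is fastest. Swapping 6 and 7 between BL and B leaves the power of that contrast unchanged.

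**1. The plan's own figure.** The SD of the means (5, 6, 7) is √(2/3) = 0.8165, so f = 0.8165/1, which the plan rounds to 0.82. Noncentral-F power with three groups is 80.5% at N=18 and 99.9% at N=45. The stated N=18 reproduces, for exact times.

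**2. What the schedule records.** P(recorded at 5) = Φ(5 − mean), where Φ is the standard normal distribution function:

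| Arm (true mean) | Recorded at 5 | Recorded at 10 | Recorded mean | Recorded SD |
|---|---|---|---|---|
| L (5) | 50.0% | 50.0% | 7.5 | 2.5 |
| BL (6) | 15.9% | 84.1% | 9.2 | 1.8 |
| B (7) | 2.3% | 97.6% | 9.9 | 0.8 |

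At most 0.13% in any arm fall later than 10 minutes. The recorded gap between L and BL is 1.7 minutes and between BL and B 0.7, instead of 1.0 each. With 15 per arm, the BL-versus-B comparison rests on about 15 × 0.159 = 2.4 against 15 × 0.023 = 0.3 patients at T10 by 5 minutes.

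**3. Power** (simulation, 40,000 trials per scenario):

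| Test | Exact times | 5-minute checks |
|---|---|---|
| Overall ANOVA, N=18 | 81% | 42% |
| Overall ANOVA, N=45 | over 99% | 86% |
| L vs B, 15 per arm | over 99% | 93–94% |
| L vs BL, 15 per arm | 75% | 54% |
| BL vs B, 15 per arm | 75% | 15% |

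Exact enumeration of T10 by 5 minutes (15.9% vs 2.3%, 15 per arm) also gives 15% for BL vs B with the t-test or Pearson's test, and 5% with Fisher's test. On the 5-minute schedule the t-test for BL vs B has 50% power at 30 per arm, 70% at 45 and 80% at about 60.

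**4. Position of the means** (same 1-minute gaps and SD 1, N=45, 5-minute checks):

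| True means (L/BL/B) | Overall ANOVA | BL vs B |
|---|---|---|
| 4/5/6 | 97% | 54% |
| 4.5/5.5/6.5 | 95% | 40% |
| 5/6/7 | 86% | 15% |
| 5.5/6.5/7.5 | 62% | 2% |
| 6/7/8 | 35% | under 1% |
| 6.5/7.5/8.5 | 16% | 2% |
| 7/8/9 | 34% | 15% |
| 8/9/10 | 86% | 54% |
| 9/10/11 | 97% | 55% |

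With exact times every row would be over 99% and 75%. With 1-minute checks every row is over 99% and about 72%. With 2-minute checks every row is about 99% and 61–64%.

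**5. Larger SD** (means 5/6/7, 15 per arm, BL vs B):

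| SD | Exact times | 1-minute checks | 5-minute checks |
|---|---|---|---|
| 1.5 | 42% | 41% | 23% |
| 2 | 26% | 25% | 19% |
| 2.5 | 19% | 18% | 15% |

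**The case against.** The strongest reply is that section 11.0 specifies one test, the overall ANOVA, and that this test keeps 86% power at N=45 on the 5-minute schedule, above the stated 80%. The rise from 18 to 45 was meant for inaccuracy and absorbs the loss. No pairwise power is claimed, and BL vs B was below 80% even with exact times. All of this is correct. It does not settle the matter, because the protocol's own interpretation depends on BL vs B, and the 86% holds only near the assumed means: a shift of one minute later takes it to 35%.

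A second reply is that SD 1 may be too small. Section 2.0 gives onset ranges of "5-15 vs. 10-20 minutes for epidural injection" for lidocaine and bupivacaine, which suggest later and more variable times. At SD 2 the schedule costs BL vs B only 7 points (26% to 19%), although the overall ANOVA still falls from about 65% to 48%. With illustrative means of 10/12.5/15 and SD 2.5, the schedule costs little overall (99.9% to 99%) and BL vs B goes from 75% to 63%. This stands as a limit: the size of the loss, and the gain from finer checks, depend on the plan's inputs being right. Section 2.0 does not say what its onset ranges measure, so they do not replace those inputs.

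Third, the arm assignment is inferred. If BL and B held the means 5 and 6, that contrast would keep 54%. Finally, 72% with 1-minute checks assumes error-free readings and is a best case.

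**Conclusion.** The concern holds. On the plan's own means and SD, with L=5, BL=6 and B=7, 5-minute checks turn time to T10 into a nearly binary outcome and cut BL-versus-B power at 15 per arm from 75% to about 15%. A true 1-minute advantage would then be missed about 85% of the time. The overall ANOVA stays above its 80% target at exactly these means, but only because N was raised from 18 to 45. Depending on where the means fall relative to the checks, it ranges from 16% to 97% over the positions examined. The conclusion rests on normal times, SD 1, the inferred order of the arms and unadjusted pairwise t-tests. A larger SD shrinks the part of the loss due to the schedule. Because the defect lies in how the primary outcome is measured, it needs to be corrected before enrolment.

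**What to change.** In sections 4.0 and 8.0, have the same blinded investigator test the pin-prick level every 1 minute, and at most every 2 minutes, from T0 until T10 is reached, and record that time as the primary outcome. Keep the 5-minute schedule for ice, motor block, blood pressure, heart rate, fetal heart rate and maximal spread. In section 11.0, state the power for the schedule adopted, both overall and for BL vs B.

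If the 5-minute schedule has to stay, analyse the times as interval-censored, restate both powers for that schedule, and say plainly that this handles grouped times correctly but does not recover the lost BL-versus-B power. Comparing the proportions at T10 by 5 minutes, for example, gives 5% (Fisher), 15% (Pearson) or 31% (likelihood ratio, with type I error about 7%).

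The cost is protocol wording and a new data sheet; the investigator already collects data through the 20 minutes. The downside is more pin-prick tests in a labouring patient, made by someone who is also recording the other measures. At mean onset of 5–7 minutes this averages about 5–7 extra tests with 1-minute checks, or 3–4 with 2-minute checks. If onset approaches 20 minutes, the maximum is 20 − 4 = 16 extra with 1-minute checks, or 10 − 2 = 8 with 2-minute checks, since those at 10 and 20 are already scheduled. Two-minute checks roughly halve the burden and cost about 9 points of BL-versus-B power (63% against 72%).

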Given that there is limited and conflicting evidence for the usefulness of the bupivacaine and lidocaine mixture especially as it relates to labor epidural activation, we hope to readdress these questions in an effort to determine whether or not the LA combination offers any distinct advantage over the individual LA. In contrast to Sinatra et al's study, we intend to determine the time it takes to achieve an adequate level (T₁₀) for labor analgesia, the total spread of local anesthetic (both caudal and rostral), and the time it takes to develop hypotension – not just the overall incidence – as these factors will be important in determining the most optimal LA solution to activate a labor epidural. We will also reevaluate the degree of motor block, as patients in Sinatra's study received a much higher concentration of bupivacaine (0.5%) than we use for epidural activation (0.125%). With the results of our study, we hope to recommend a LA solution that will allow for the fastest pain relief in the laboring mother with the fewest side effects.

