6.0 RANDOMIZATION/RECRUITMENT PROCEDURES

Patients who are admitted to the labor and delivery (L&D) suite at the Women and Infants' Center (WIC) for induction of labor will be approached about recruitment into the study. The recruitment process will begin prior to any obstetric intervention that may induce pain or altered mental status to the patient.

As this will be a double-blinded study, the randomization process will be performed by someone other than the investigator gathering the data. Cards containing the LA to be given along with a code will be placed in a sealed envelope and numbered. There will be an equal number of patients randomized to each group. A card will be chosen by the anesthesia provider performing the procedure. The provider will administer the LA solution the patient is randomized to receive. The provider will write the code from the card on the data sheet. The code will be used to identify the LA solution given.

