If, on administration of the test dose, the epidural catheter is believed to be intravascular (increase in HR > 20% above baseline) or spinal (an acute anesthetic level is noted by hip flexor weakness), then the catheter will be deemed not safe to use, and the patient will be removed from the study. The epidural catheter can be replaced by the anesthesia provider; however, since the data will be flawed from the initial positive test dose, the patient will not be allowed to participate in the study at that point. Also, if the patient does not receive an anesthetic level from the initial bolus plus infusion after 20 minutes, the epidural catheter will be documented as a failed catheter, and the patient will be removed from the study. The anesthesia provider will replace the epidural catheter in standard fashion if the patient requests to have it replaced.

The endpoint for our primary outcome will be the time it takes to achieve the T₁₀ level to pin prick, which should occur before 20 minutes; however, we will continue to monitor the patient throughout the 20 minute interval to determine the maximal spread of the LA (via measurement of the dermatome level by pin prick and ice), the degree of motor weakness, and if any hypotension occurs. During this time, the patient will have standard monitoring that all patients in labor receive: non-invasive BP and pulse recording and non-invasive FHR tracing. The L&D nurse, obstetricians, and anesthesiologists involved in the patient's care will deliver the same standard of care given to all patients on the L&D floor. Once the study is complete (after 20 minutes), the patient will continue to receive LA infusion through the epidural catheter throughout the remainder of labor and delivery. The anesthesia provider will continue to care for the patient throughout the patient's labor and delivery.

On average 5 to 10 patients are scheduled for induction each week. If 60% are consented for the study, then it should take approximately 3 months to enroll 45 patients.

Projected Overall Study Timeline

	Study Start-Up	Enrollment	Data Entry and Analysis	Study Write-Up
MM YYYY	08/2014			
MM YYYY		08/2014-11/2014		
MM YYYY			11/2014	12/2014

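### Vasopressor doses are recorded without their time or the blood pressure that prompted them, so hypotension treated between scheduled readings can be confirmed and dated only indirectly

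*Combined protocol and SAP*

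**What the plan says.** Section 4.0 lists as a secondary outcome the "incidence of maternal hypotension defined as a BP >20% decline from baseline". Section 8.0 repeats that definition and lists vasopressor need and vasopressor amount as separate outcomes.

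For data capture, section 8.0 has the investigator record blood pressure at the bolus (T0) and at 5, 10, 15 and 20 minutes, adding at the later times "any vasopressor (phenylephrine or ephedrine) required to treat maternal hypotension and the dose". The agent and dose are named; the time of the dose and the pressure before it are not.

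The same section states that "we will continue to monitor the patient throughout the 20 minute interval", among other reasons to see "if any hypotension occurs". Standard non-invasive blood pressure recording is in place, but its frequency is not given.

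Two other sections rely on these data. Section 2.0 wants to determine "the time it takes to develop hypotension", and not merely how often it happens. Section 5.0 (Interpretation of Expected Results) plans to compare side-effect profiles "By measuring the incidence of hypotension and degree of motor blockade".

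**The concern.** The outcome is defined by a pressure, but the recording instruction ties pressures to five time points. Suppose a clinical cuff reading between two of those points shows a fall of more than 20%, a vasopressor is given, and the pressure has recovered by the next scheduled reading. The study data then hold an agent and a dose, but no pressure that meets the definition and no time. Whoever builds the outcome later must decide, without the qualifying reading, whether that patient had hypotension and when.

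At stake are a secondary outcome that feeds the recommendation on the best solution, and the stated aim of timing hypotension. The missing items are easy to note at the bedside and may not be recoverable afterwards, so an analysis choice cannot replace them.

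**Working it through.** **The plan's own figure.** Section 11.0 gives a total N of 18 for the primary outcome. The inputs there are means of 5, 6 and 7 minutes, variance 1, alpha 0.05 and 80% power. The standard deviation of the means is √[((−1)² + 0² + 1²)/3] = 0.816, so f = 0.816/1 = 0.82. With the noncentral F distribution (3 groups, noncentrality N·f², f = 0.82), power is 0.705 at N = 15 and 0.809 at N = 18. The figure reproduces, and the target of 45 gives power 0.999. None of this depends on how hypotension is recorded. The plan states no figure for hypotension.

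**What each kind of fall leaves in the data.** Setting the definition (sections 4.0 and 8.0) against the recording instruction (section 8.0):

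- *Fall of more than 20% present at a scheduled reading:* a qualifying pressure is recorded and the event counts.
- *Fall seen between readings, treated with a vasopressor, corrected by the next reading:* agent and dose are recorded, but the instruction calls for no qualifying pressure. The event can be inferred from the vasopressor entry, not confirmed against the definition.
- *Fall seen between readings and treated with crystalloid alone* (section 9.0 names crystalloid as routine treatment): section 8.0 requires no entry.
- *Fall between readings that no cuff measurement sees:* nothing is recorded, and nothing could be.

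Only the second kind is at issue here.

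**Dating the onset.** Scheduled readings are 5 minutes apart. If the vasopressor is entered at each documentation time, a dose first entered at 10 minutes was given after the 5-minute reading. With a normal reading at 5 minutes, onset lies somewhere in a window of 10 − 5 = 5 minutes. As an illustration with an assumed dose time, a recorded dose at minute 7 with a qualifying pressure just before it narrows the window to 7 − 5 = 2 minutes.

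**Size per patient.** Section 11.0 plans 15 patients per arm. One patient counted or not counted moves an arm's incidence by 1/15 = 0.067, that is 6.7 percentage points.

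**Total size.** This would need the hypotension rate, the share of falls treated between readings, how long a treated fall lasts, and how often the cuff is read. The documents give none of the four, so no expected undercount follows from them.

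**The case against.** The case on the other side is substantial.

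*Treatment is tied to the event.* Section 4.0 describes the vasopressor as given for the hypotension it has just defined, and section 8.0 uses similar words. A recorded vasopressor is thus naturally read as marking a hypotensive patient. This stands in part: most such patients leave a trace, usually placed within about 5 minutes, and they still count under vasopressor need and amount. It is not a counting rule, however, and without the pre-dose pressure nobody can check that the 20% threshold was met.

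*The whole 20 minutes is monitored.* Section 8.0 commits the team to looking for any hypotension, and the definition is not restricted to scheduled readings. That stands as intent. The section does not say that readings between the scheduled times are written down as study data.

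*The form may already ask.* Section 6.0 mentions a data sheet that is not among the documents. It may have a field for dose time. If so, the point reduces to stating this in the protocol.

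Three stronger readings are tempting, and the documents do not support them.

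- A reader might infer that treated falls will be left out of the incidence. The two arguments above show that the plan allows them to be counted; what is missing is the evidence to do so directly.
- A reader might compute a loss rate. With 5-minute gaps and uniform onset, a fall lasting d minutes misses every scheduled reading with chance 1 − d/5, for example 40% at 3 minutes. But the duration is assumed, and the formula includes falls that no cuff would see. If one extra cuff reading is assumed midway between scheduled times, a 1-minute fall misses the schedule 80% of the time but is seen by that extra reading only 20% of the time. If the cuff is read only on schedule, there is nothing between readings to recover.
- A reader might infer bias between arms, because "A card will be chosen by the anesthesia provider performing the procedure" and that provider therefore knows the solution given. No section says who orders vasopressors or at what pressure, so treatment that depends on the arm is possible but not shown.

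**Conclusion.** The point holds as a gap in data capture. Hypotension treated and corrected between scheduled readings can be confirmed only through the vasopressor entry, and its onset is known only to about 5 minutes. The second part assumes that vasopressors are entered at each documentation time. The whole point assumes that cuff readings are sometimes taken off schedule and that the data sheet asks for no more than section 8.0 does.

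Each affected patient is worth 6.7 points of an arm's incidence; how many there would be is unknown. Time to hypotension is an aim in the background section but appears in none of the secondary outcome lists, which limits the weight of the dating problem. The point affects a secondary outcome and leaves the primary outcome and N unchanged, so it is a cheap improvement of low severity.

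**What to change.** In section 8.0, add two items for every vasopressor dose: its clock time and the blood pressure immediately before it. Then state the counting rule. A fall of more than 20% from baseline at any scheduled or pre-dose reading is hypotension, and onset is dated from the first such reading. This matches the section's own intent to detect any hypotension in the 20 minutes.

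Also report incidence at the scheduled readings alone as a check. Those readings are taken on the same schedule in every arm, whereas pre-dose readings exist only when a clinician chooses to treat.

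The cost is two entries per dose and one extra reported line, with blood pressure recording already in place. The downside is small: the fuller count depends partly on treatment decisions, which the scheduled-only check helps to expose. The change does not recover falls treated with crystalloid alone, or falls treated before they reach 20%.
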